LHWs will carry out home visits in pairs or with 3 LHWs dependent on the needs of that household. A LHW employed by the clinics will provide routine contact investigation services and a trained study LHW will collect research data and deliver the intervention for those randomized to the intervention arm of the study. While the LHW carries out standard contact investigation screening, the study LHW will administer a short HIV-TB stigma scale individually to all consenting adult members of the household in both arms. The research LHW will follow the assigned script based on randomization allocation to identify household members who are eligible and invite them to test for HIV, recording time-stamped offers, test decisions, and test results. The research LHW will collect household- and individual-level demographic, socioeconomic data, stigma scales, measures of household stability, including household tenure in years as well as relationship to and perceived influence of household members and clinical data using a structured survey.

Procedures for all households: Upon arrival, the CHWs will enroll all eligible, consenting household contacts in the study. But before doing this, at the start, CHWs will introduce themselves and ask for introduction of contacts. At this time the master list of all the contacts will be created.

- They will introduce the reason for their visit and the services they will offer (TBCI, oral HIV testing) using the introductory script for either Intervention or Routine Contact Investigation households, depending on the household assignment.
- For the intervention arm, one CHW will take the index case to a private area to ask the influence questions using the paper form (master list) as a key. After completing this exercise, the CHW will then embark conducting household contact screening interviews followed by HIV testing and any other study related activities. All data will be collected via CommCare.
- Meanwhile, the other CHW will be conducting routine TB contact investigation activities and any other clinical procedures in household TB contact investigation. Details of these procedures are found below:

a) Index case influence questions

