After enrollment, CHWs will introduce themselves and ask for the introduction of contacts and it is at this time when a contacts master list will be created. Index patients will then be asked the influence questions. The questions will be asked in two steps, once to capture the number and once to capture the name. The other CHW will go head to conduct routine TB contact investigation activities.

b) Household contact screening interview

After household contact enrolment, each contact will undergo a short interview. This interview will capture age, gender, occupation (if applicable), income (if applicable), education in years, relationship to index patient, history of testing for HIV, month and year of last HIV test, and self-reported symptoms of TB (including cough, subjective fever, or weight loss).

The short (13-item) version of the Van Rie TB- and HIV-related stigma scales will be administered immediately prior to TB screening, as well as at the conclusion of the visit. We will ask the index patient to share the number of rooms in the dwelling, the number of windows in the dwelling, and the number of individuals (including children) who dwell there. All screening interview components will be conducted by a CHW. Screening interview components are identical for all study groups.

c) HIV testing procedures

Working in teams of two, CHWs will provide household contact investigation services, including offering oral HIV testing. One CHW will lead and accompany each HIV test while a colleague leads other household members through TB screening.

To begin, the CHW responsible for offering HIV testing will individually invite the client to a place apart from the others. S/he will detail the process of HIV testing in Luganda and/or English, per client preference. A pictorial guide may be used to help walk the client through each step of the process using a Luganda- or English-language guide. The CHW will then provide pre-test counselling.

Consenting household contacts who choose to test for HIV will swab their own gums. CHWs will be fully trained to provide HIV counselling and support throughout all testing procedures.

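### As written, an arm-dependent introduction comes before contacts enrol and before the first stigma scale, so any effect it has is left out of the primary change score

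*Combined protocol and SAP*

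**What the plan says.** All places are in Section I of the combined protocol and SAP; subsections are in 4. Research Plan unless stated.

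- **Randomization.** The household is allocated by telephone once the index patient has consented. The team for that arm is then contacted for the visit, and each visiting team works in one arm only.
- **Procedures for all households.** The first sentence has the team enrol consenting contacts on arrival. The text then continues: "But before doing this, at the start, CHWs will introduce themselves and ask for introduction of contacts". The first bullet has the team explain why it has come and what it offers, "using the introductory script for either Intervention or Routine Contact Investigation households, depending on the household assignment". The next bullet reads "For the intervention arm, one CHW will take the index case to a private area to ask the influence questions", and then "After completing this exercise, the CHW will then embark conducting household contact screening interviews followed by HIV testing".
- **a) Index case influence questions.** "After enrollment, CHWs will introduce themselves and ask for the introduction of contacts"; then "Index patients will then be asked the influence questions". No arm is named and no script is mentioned.
- **b) Household contact screening interview.** The interview follows enrolment of the contact. The 13-item scales "will be administered immediately prior to TB screening, as well as at the conclusion of the visit". It adds: "Screening interview components are identical for all study groups".
- **TB and HIV stigma scales** puts the first administration at the start of the home visit. **1. Statement of Purpose, Aim 2** puts it before the invitation.
- **Analysis** makes change in perceived HIV-TB stigma the primary outcome and uptake of HIV testing the secondary outcome.

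**The concern.** A change score measures only what happens between its two readings. If contacts hear wording that differs by arm before the first reading, any response to it is already in the baseline. A benefit would be understated, and a rise in stigma would not appear in the change score.

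The plan's own rationale makes this worth attention. The opening of the Research Plan argues that minor differences in the manner of offering a test can move uptake a good deal, by way of perceived stigma. The CHW Training paragraph has each team rehearse its own procedures separately, and nothing states that the two introductions are equivalent.

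Contacts also decide whether to enrol after hearing the introduction. If it affects that decision, the enrolled groups could differ by arm. Uptake would then be affected if it is calculated among enrolled contacts.

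**Working it through.** **Order of events.** Putting the subsections together gives:

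1. Index consent and randomisation.
2. Visit by the arm's own team.
3. Introduction with the arm's script, and listing of contacts.
4. Enrolment of contacts.
5. Screening interview with the first scale.
6. Test offer, testing and counselling.
7. Second scale.

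The first scale is given only to consenting members (Household-Randomized controlled trial), so it cannot precede step 4. The looser timings (start of the visit, before the invitation) do not place it ahead of step 3. The sentence on identical components concerns the interview itself, not what contacts heard before it.

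**What each comparison captures.** Let d1 be the between-arm effect of the introduction, assumed to persist to the end of the visit, and d2 the effect of everything after the first scale.

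- First-scale difference between arms: d1
- End-of-visit difference: d1 + d2
- Difference in change: (d1 + d2) − d1 = d2

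The change score therefore keeps the share 1 − f, where f = d1/(d1 + d2).

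**The plan's own sample size.** It reproduces, but it concerns uptake, not stigma. Inputs: 0.85 vs 0.98, power 90%, alpha 0.05 (two-sided assumed), ICC 0.59.

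- Contacts per arm before clustering: [1.960·√(2·0.915·0.085) + 1.282·√(0.85·0.15 + 0.98·0.02)]² / 0.13² = 94.6
- Two contacts per household: 94.6 × 1.59 / 2 = 75.2, so 76 per arm, 152 in total
- Three contacts per household: 94.6 × 2.18 / 3 = 68.8, so 69 per arm, 138 in total

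Both match the plan. No stigma effect size, standard deviation or power is given.

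**Stigma illustration (every share assumed).** Power on change = P(Z > 1.960 − k(1 − f)), with k = 1.960 + 1.282 = 3.242 if the full effect had 90% power, or 1.960 + 0.842 = 2.802 if it had 80%.

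| f | full-effect power 90% | full-effect power 80% |
|---|---|---|
| 0 | 90% | 80% |
| 0.05 | 87% | 76% |
| 0.10 | 83% | 71% |
| 0.25 | 68% | 56% |

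If a model instead adjusted for the first scale with slope b, the retained share would be 1 − b·f. At f = 0.25 and 90% full-effect power, b = 0.5 gives 81% and b = 0.7 gives 76%.

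**Uptake illustration (assumed counts; denominator taken as enrolled contacts).** At control uptake of 0.85, 15 of 100 contacts decline.

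- If 1, 2 or 3 of those 15 stay out in the intervention arm only: 85/99, 85/98, 85/97 = 0.859, 0.867, 0.876, a spurious +0.9, +1.7, +2.6 points.
- If 1 or 3 extra contacts enrol and then decline: 85/101 = 0.842 and 85/103 = 0.825, or −0.8 and −2.5 points.
- Bound: 85/(100 − x) = 0.98 gives x = 13.3. About 13 of the 15 would have to stay out for selection alone to produce the planned effect.

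**The case against.** The strongest reply is that the harm rests on text that the documents do not contain. The introduction is described only as covering the purpose of the visit and its services, and oral testing is offered in both arms. The components under Specification of intervention components (choice of first tester, prosocial line, opt-out line, sharing the decision) come at or after the test offer, which c) HIV testing procedures makes individual and private. This stands. A reader might infer that the intervention proper is delivered before baseline; the documents do not support that.

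Three other strong readings also fail.

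- **That the order is contradictory.** The words after enrollment in a) do not say whose enrolment. Read as index enrolment at the clinic, they agree with Procedures for all households. This needs clarifying and is not a firm contradiction. On either reading the introduction precedes the interview that carries the scale; only the enrolment concern depends on which reading is right.
- **That the analysis cannot recover the loss.** Households are randomised before the visit. A between-arm comparison of end-of-visit scores, unadjusted for the on-visit baseline, captures the introduction's effect with the rest, provided enrolment does not differ by arm. A comparison of first-scale scores by arm bears directly on d1.
- **That the influence questions contaminate the baseline.** They are put to the index patient in private, and no effect on contacts' scores is claimed.

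On uptake, 13. Statistical Considerations specifies intention to treat, and the visit's master list is drawn up before contacts enrol. That helps, but the list is made by an arm-aware team, and the plan does not say whether uptake is calculated over listed or enrolled contacts.

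**Conclusion.** The concern holds in a limited form. As written, an arm-specific team delivers an arm-dependent introduction before contacts enrol and before the first stigma scale, and no other subsection moves the scale ahead of it. Any effect of that wording would be missing from the primary change score, and the wording could also shape who enrols.

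Neither size nor direction can be estimated from the documents. The effect may be small, and if the two introductions are equivalent it is nil. The power and uptake figures above rest wholly on assumed shares and show only how sensitivity grows with the share. By the bound shown, selective enrolment is unlikely to produce the planned uptake difference by itself. The change is still worth making, because it is cheap and protects the baseline of the primary outcome. Confidence is medium.

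**What to change.** - Use one identical, neutral introduction in both arms until contacts have consented and completed the first scale. Give any arm-specific wording only after that.
- State this single order in Procedures for all households, in a) and b) beneath it, and in TB and HIV stigma scales. Say whose enrolment a) means.
- Add a sensitivity analysis comparing end-of-visit stigma scores between randomised arms without adjustment for the on-visit baseline, and compare first-scale scores by arm.
- Report enrolled over listed eligible contacts (aged 15 or older) by arm, using the household composition that the index patient gives at enrolment.
- Separately, reconcile when and in which arm the influence questions are asked. Procedures for all households places them at the visit in the intervention arm, a) names no arm, and both Household-Randomized controlled trial and Specification of intervention components place influence at index enrolment.

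The cost is a script edit, brief CHW retraining and a few extra table rows; the household composition is already collected. A group-level intervention message remains possible after the first scale. Arm-aware teams would still enrol contacts and give both scales, so the risk is reduced but not removed.

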Randomization: For aim 2 of the study, variable block randomization will be done at the level of the household and will be performed at the time of household enrollment. Block sizes will have a minimum of 2, a maximum of 6. We will utilize study randomizer, an online randomization tool with concealed randomization. When a CHW has deemed an index patient and their household to be eligible for the study, and after the index patient or their guardian has provided verbal informed consent, the CHW will place a phone call to the study coordinator. The study coordinator will then enroll the household using the study randomizer tool and let the CHW know the study allocation. The CHW will then fill in the appropriate allocation, along with the randomization ID, and contact the appropriate CHW team for the household visit.

Households randomized to intervention group will be offered oral testing with the social-behavioral intervention. Households randomized to the standard of care group will be offered oral testing without any social-behavioral intervention. CHWs will operate in teams that are always assigned to the same arm of the study. There will be three teams of CHWs in total: one intervention group, one standard of care group, and one clinic-based group that will always be in charge of initial enrollment of index patients and recording any clinic follow up by individuals in either arm of the study.

Integrated intervention. In Intervention Households only, the CHW will present the opportunity to test using the script and procedures described in the next section (“Specification of intervention components”). This script communicates that the individual is completely free to opt out of testing, but that testing is the norm. We will use “Opt-Out” testing language along with language letting them know that they can decline.

If the household contact decides to opt out of HIV testing, the CHW will carry out a survey. These questions will take approximately the same amount of time as HIV testing and counselling procedures (~20 to 30 minutes) in order to blind other household members from the testing decision of that household contact. Contact decisions to test or not to test as well as test results will be recorded in CommCare.

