TB and HIV stigma scales Study CHWs will individually administer the short-form HIV-TB stigma scales to all study participants regardless of group using the CommCare application alongside a visual aid. These scales have a total of 13 items and were validated in the Uganda setting as part of the Aim 1 procedures. The scales will be administered first at the beginning of the home visit, then again at its conclusion. Each time, the CHW will briefly orient the participant to the response categories using a visual aid.

Documentation and Data management All enrollment procedures, household contact interviews and HIV testing details will be collected using CommCare. All forms will be available within a customized CommCare application that prevents common errors (such as not filling out a question etc.). Quality control procedures will include review of all study data collection forms for completeness and accuracy, including quality assurance testing of all validation and skip logic within the application, prior to study initiation. The US study coordinator will initiate reports on missing data and provide feedback to all study team members on the quality of quantitative data. All changes will be recorded using a data management google doc tracking sheet that contains information on the change, who made the change and a link directly to the location of the change on CommCare. Any duplicate cases (i.e. two cases for one index patient or contact) will be archived and similarly recorded.

Follow-up interview. At 3 months, the study LHW or a member of study team will contact a subset of households to schedule a follow-up visit or phone call if a second visit is unable to occur. The study LHW or a member of the study team will re-administer stigma scales to each participating member. Household members who are not present at the second household visit will be contacted by telephone to schedule a follow-up interview.

Sample Size.

During aim 2, we will distribute the stigma scales up to approximately 152 households containing approximately 304 household contacts with approximately 1:1 randomization (half in each study arm). We analyzed power for a 2-arm household-randomized, controlled trial using mixed models tests for two proportions in a two-level hierarchical design (household, contact). The assumptions and parameters within these calculations were based on data from Aim 1 and include:

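### The clinic team that enrols every index patient is told each household's arm after consent and later records clinic follow-up unmasked; this modest, avoidable weakness is cheap to remove

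*Combined protocol and SAP*

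**What the plan says.** The Randomization paragraph (Section I, item 4, Procedures for Aim 2) states that "variable block randomization will be done at the level of the household and will be performed at the time of household enrollment". On block size: "Block sizes will have a minimum of 2, a maximum of 6". On concealment: "We will utilize study randomizer, an online randomization tool with concealed randomization".

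The sequence is as follows. Once a household is judged eligible, and "after the index patient or their guardian has provided verbal informed consent, the CHW will place a phone call to the study coordinator". Then: "The study coordinator will then enroll the household using the study randomizer tool and let the CHW know the study allocation". Then: "The CHW will then fill in the appropriate allocation, along with the randomization ID, and contact the appropriate CHW team for the household visit".

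The next paragraph describes three CHW teams. Two are tied to an arm. The third is "one clinic-based group that will always be in charge of initial enrollment of index patients and recording any clinic follow up by individuals" in both arms. The CHW Training paragraph confirms that the clinic-based team handles index enrolment and randomization procedures.

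Four other statements bear on the point:

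- The trial paragraph says about 152 index patients will be enrolled consecutively, at 2 TB units.
- The same paragraph has demographic and household-composition data collected on consent, and the home visit scheduled after enrolment.
- Aim 2 lists linkage to HIV care at 1 month as a measured outcome, and the Analysis paragraph says it will be assessed descriptively.
- Under the procedures for all households, contacts are enrolled at the home visit, after the household has been allocated.

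The plan does not say whether the list is stratified by unit, whether block sizes are kept from CHWs, or whether the clinic team is masked.

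**The concern.** A central concealed tool hides the next assignment at the moment of the call. It does not hide past assignments, and this procedure hands each of those to the staff who judge eligibility and seek consent. In a blocked list, past assignments carry information about the next. A recruiter who expects a given arm can invite more or less warmly, or sooner or later. The intention-to-treat analysis in item 13 cannot undo selection that happens before randomization.

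Two further effects need no guessing. First, if the arm is known before the contact list and visit slot are settled, it can influence both. Visit timing helps decide who is at home, and therefore who is enrolled and who can be invited first. Second, clinic follow-up is recorded by people who know which households had the intervention, so prompting or searching could differ between arms.

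**Working it through.** **Inputs.** Blocks run from 2 to 6 (Randomization paragraph). With 1:1 allocation I read these as sizes 2, 4 and 6. Their mix is not stated, so I assume equal frequency and then vary it. The list length is 152 households (Sample Size). The trial paragraph gives 2 enrolling units, while the routine data paragraph mentions 4. Stratification is not stated.

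**The plan's own figure.** The pooled two-proportion formula (two-sided 0.05, 90% power, 0.85 against 0.98) gives 94.6 contacts per arm.

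- Mean of 2 contacts: 94.6 × (1 + 0.59) / 2 = 75.2, so 76 per arm and 152 households.
- Mean of 3 contacts: 94.6 × (1 + 2 × 0.59) / 3 = 68.8, so 69 per arm and 138 households.

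Both match the plan, and neither is in dispute. The plan gives no figure for predictability.

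**1. Whole list seen.** The guesser names the arm currently behind and tosses a coin when the arms are level. Every block ends level, so the running imbalance of the whole list is that of the current block, and the rule needs no knowledge of block sizes. For a block of 2k, the expected number of correct guesses is k + ½[4^k / C(2k, k) − 1].

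- Size 2: 1 + ½(4/2 − 1) = 1.5 of 2, or 75%
- Size 4: 2 + ½(16/6 − 1) = 2.833 of 4, or 70.8%
- Size 6: 3 + ½(64/20 − 1) = 4.1 of 6, or 68.3%

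Equal mix: (1.5 + 2.833 + 4.1) / 12 = 8.433 / 12 = 70.3%. A simulation of 2,000 lists of 152 used the best guess for someone who knows the possible sizes but not the size of each block. It gives 70.2% correct, with 4.1% of assignments certain. Other mixes within 2 to 6 give 70-71% correct and 3-7% certain. With a known fixed size, the certain share would be 50% (size 2), 33.3% (size 4) or 25% (size 6). Varying the size therefore removes most of the certainty but little of the predictability.

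**2. Part of one shared list seen.** I simulated 4,000 lists under two simple rules: guess from the imbalance among the allocations seen, or guess the opposite of the last one seen.

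- Half the list seen: 52.7% and 58.3%
- A quarter seen: 51.6% and 54.9%

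If the list is stratified by unit, each unit's staff see their whole list and step 1 applies. It also applies if the team pools what it knows.

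**3. What would lower it.** Sizes 4/6 give 69.2%, 4/6/8 give 68.0% and 6/8/10 give 66.3%. Withholding past arms from the recruiters gives about 50%.

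**4. Order of tasks.** The Randomization paragraph puts the call after consent, at household enrolment. The trial paragraph puts household composition on consent and visit scheduling after enrolment, and mentions random assignment only afterwards. Nothing requires the contact list and visit slot to be final before the arm is known.

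**5. Scale for linkage (illustrative).** Assume the national 7.1% prevalence in the Background applies to all 304 contacts and that all of them test: 0.071 × 304 = 21.6, or 10.8 per arm. If between 25% and 100% of these are new diagnoses, that is 2.7 to 10.8 per arm. One case more or fewer recorded as linked would then move an arm's proportion by 1/10.8 = 9 to 1/2.7 = 37 percentage points.

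**The case against.** Telling the recruiter the arm after consent, with central allocation, is common in open trials, and the plan has real safeguards. Eligibility and consent come first, the coordinator runs the tool, block sizes vary, eligibility rests on routine screening answers, and patients are to be consecutive. These points stand, and they limit the harm. They leave some discretion over how and when to invite, and the plan describes no screening log against which consecutive enrolment could be checked.

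The 70% is an upper bound. It needs sight of the whole list, which the plan neither states nor rules out. A reader might also infer from the minimum block of 2 that arms are guessed 75% of the time and that half are certain. That would be a design with every block of size 2, which is not this one.

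Linkage is descriptive, so unmasked recording reaches no hypothesis test. The plan does not say that 1-month linkage comes from this team's records; the Referral protocol also gives clients a slip and a number to call on reaching the clinic. This stands too, though a descriptive proportion meant to inform a later trial still benefits from even-handed recording.

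Finally, the larger exposure lies elsewhere. Arm-specific teams enrol the contacts and record stigma and testing after allocation. That is correct. It is a separate problem, and no reason to leave this one open.

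**Conclusion.** The point holds as a cheap improvement. The enrolling team learns each arm after consent, can guess the next arm somewhat better than chance, may know the current arm before the contact list and visit slot are fixed, and records clinic follow-up knowing the arm.

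Against 50% by chance, the guessing rate is at most about 70% (whole list seen) and about 52-58% with a partial view of one shared list. Even with the whole list in view, only about 4% of arms are certain. These figures assume blocks of 2, 4 and 6 used equally often; other mixes change them little. Which end applies depends on stratification and pooling, which the documents leave open.

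A reader might go further and conclude that concealment has failed, that the team hand-picks households, or that a tested outcome is biased by unmasked follow-up. The documents do not support this. Each arm is drawn after consent by a concealed tool, enrolment is meant to be consecutive, and linkage is descriptive with no stated data source. No figure in the plan is shown to be wrong.

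**What to change.** Amend the Randomization paragraph as follows:

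- The enrolling CHW completes eligibility, consent, the contact list and the visit slot in CommCare before calling the coordinator, and receives only the randomisation ID.
- The coordinator sends the allocation directly to the assigned field team.
- The arm field is hidden from the clinic team's CommCare login, so that clinic follow-up is recorded masked where possible.
- Block sizes are kept out of documents that CHWs see. This removes the few certain guesses but not the 70%, which needs no knowledge of block size. Dropping size 2 is optional and changes little (70.2% to 69.2%).

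State also whether the list is stratified by unit and where 1-month linkage data come from.

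The cost is one more message per household for the coordinator (about 152 in all) and a form permission, with no extra staff. Visit slots must be ones that either field team could keep, because the slot is set before the arm is known. Masking will sometimes fail, since patients talk and clinic-employed LHWs join home visits. The change does not address contact enrolment and outcome recording by arm-specific teams after allocation, which need separate attention.
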